2.2 Randomization

Randomization is performed using a web-based system (Clinsight® software). Patients are randomly assigned in a 1:1 ratio to one of the two groups using a minimization algorithm based on three determinants: study site, initial World Federation of Neurological Surgeons (WFNS) grade ([1 or 2] vs [3 to 5], higher scores being indicative of more severe aSAH), state of consciousness at the time of vasospasm diagnosis (conscious vs unconscious, including patients under sedation).

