3.1 Confidence Intervals and P-values

The statistical uncertainty of all estimates will be expressed as two-sided 95% confidence intervals. A p-value will only be reported for all the primary and secondary outcomes. A p-value <0.05 will be considered significant.

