4.3 Baseline characteristics

Baseline characteristics of randomized patients include age; sex, comorbidities, usual medication, admission ECG, hemoglobin at patient's admission, parameters of secondary brain injury (natremia min/max, body temperature min/max, mean arterial pressure min/max, ICP min/max), SAH characteristics/grade (WFNS initial score, Fisher class), Initial treatment of aneurysm (embolization and/or surgery), Consciousness at inclusion.

 CHU ANGERS <small>CENTRE HOSPITALIER UNIVERSITAIRE</small>	 Statistical analysis plan	N° EudraCT 2019-002145-37 CT Number : 2024-515994-83-00 SAP V1.0 Date : 15/01/2026
---	--	---

5 Section 5 – Analysis

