- b) Percentage of patients alive and at home at 3 and 6 months. It will also be analyzed as the number of days alive and at home at day 90 (DAAH90).
- c) angiographic success will be assessed by the evaluation of vasospasm severity on inclusion, D7 and D14 (if available) CTA. Vasospasm will be quantified according to the reduction of cerebral arteries diameter evaluated on a semi-quantitative scale as: absent, light, mild, moderate or severe, (compared to the diameter measured on admission CTA).
- d) Number of therapeutic arteriography
- e) The volume of cerebral necrosis will be measured on magnetic resonance imaging (MRI) obtained between 3 and 6 months following aSAH
- f) on adverse events evaluated until 48 hours after study medication stop.
- g) The treatment tolerance will be evaluated by assessing the rate of patients with hemodynamic intolerance defined as the need for catecholamines introduction or doses increased by 50% within the first 24 hours of study medication infusion ; and of metabolic intolerance defined as the rate of patients with dysnatremia, (ie natremia<135 mmol/L or >155 mmol/L) occurring during the administration of study medication.

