 CHU ANGERS <small>CENTRE HOSPITALIER UNIVERSITAIRE</small>	 Statistical analysis plan	N° EudraCT 2019-002145-37 CT Number : 2024-515994-83-00 SAP V1.0 Date : 15/01/2026
---	--	---

5.2.3 *Tertiary outcomes*

- The analysis of angiographic successes at day 7 and 14 will be performed considering (ordinal) proportional odds models, based on the same set of covariates
- The proportion of therapeutic arteriography between each group and the median number of arteriography will be compared.
- The analysis of hospital length of stay will be carried out by using linear regression models based on the same set of covariates.
- Patients outcomes and treatment tolerance will be analyzed using logistic models for dichotomous data (transfer to a convalescent center, patients living at home at 3 and 6 months, need to initiate or to increase the catecholamine doses by 50%, occurrence of dysnatremia), or linear regression models for continuous data (DAAH90, daily dose of catecholamines, average daily urine output).

5.2.4 *Pre-planned sub-group analysis*

We plan exploratory subgroup analyses for the primary outcome (as described above) in the following sub-groups:

- Sex: female sex versus male sex. We hypothesize no treatment effect difference between male and female sex.
- Initial WFNS score <3 vs ≥ 3 . We hypothesize that the treatment effect is more important in the less severe patients (WFNS <3).
- Consciousness level at inclusion: conscious vs unconscious. We hypothesize that the treatment effect is more important in the less severe patients (conscious patients).

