Percentage of patients alive and at home at 3 and 6 mnths	Presented as median difference with 95% CI, using quantile regression		
 median with IQR unadjusted model 	
 center, initial WFNS (<3 or ≥ 3) patient's consciousness at inclusion
DAAH90	Presented as median difference with 95% CI, using quantile regression		
 median with IQR unadjusted model 	
 center, initial WFNS (<3 or ≥ 3) patient's consciousness at inclusion
Angiographic success at D7 and D14	Ordinal logistic regression model		
 unadjusted model 	
 center, initial WFNS (<3 or ≥ 3) patient's consciousness at inclusion

 CHU ANGERS <small>CENTRE HOSPITALIER UNIVERSITAIRE</small>	 Statistical analysis plan	N° Eudract 2019-002145-37 CT Number : 2024-515994-83-00 SAP V1.0 Date : 15/01/2026
---	--	---

Number of therapeutic angiography	Presented as median difference with 95% CI, using quantile regression		
 Median with IQR unadjusted model 	
 center, initial WFNS (<3 or ≥3) patient's consciousness at inclusion
volume of cerebral necrosis on MRI done between 3 and 6 months	Presented as median difference with 95% CI, using quantile regression		Median with IQR	
Proportion of patient with hemodynamic intolerance (i.e. introduction of catecholamine or increase of ≥50% of infusion rate) within 24 hours of study medication	Log-binomial logistic regression reported as a risk ratio with 95% CI		
 unadjusted model 	
 center, initial WFNS (<3 or ≥3) patient's consciousness at inclusion
Proportion of patients with dysnatraemia	Log-binomial logistic regression reported as a risk ratio with 95% CI		
 unadjusted model 	
 center, initial WFNS (<3 or ≥3) patient's consciousness at inclusion
Daily dose of catecholamine	Presented graphically with 95% CI, per group			
Daily minimum and maximum natremia	Presented graphically with 95% CI, per group			
Daily urine output	Presented graphically with 95% CI, per group			

Unless otherwise stated, all analyses will be conducted on the Intention to treat population: includes all aSAH patients randomized.

** Adjustments for all listed analyses unless otherwise specified

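### Metabolic intolerance is estimated only as one pooled rate of low or high sodium, so a one-way sodium effect can be understated; add a rate for each direction

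*SAP*

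**What the plan says.** SAP section 5.1.3 g) gives the outcome as "metabolic intolerance defined as the rate of patients with dysnatremia, (ie natremia<135 mmol/L or >155 mmol/L", counted when "occurring during the administration of study medication".

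Section 5.2.3 lists "occurrence of dysnatremia" among the dichotomous outcomes for logistic models. Table 1 has one row for it, "Proportion of patients with dysnatraemia", with one adjusted risk ratio and 95% confidence interval. Nowhere does the SAP plan a rate below 135 mmol/L or above 155 mmol/L on its own.

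The only other planned sodium output during treatment is the Table 1 row "Daily minimum and maximum natremia", shown as graphs with 95% confidence intervals per group. Section 5.2.3 names linear models for catecholamine dose and urine output, but none for sodium.

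On testing, section 3.1 states: "A p-value will only be reported for all the primary and secondary outcomes". This outcome is tertiary, so it will be read from an estimate and its interval.

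**The concern.** A composite is easiest to interpret when treatment is expected to push its components the same way. Here the components are the two opposite tails of one laboratory measure. If milrinone moves sodium in one direction, patients leave one tail and enter the other, and the pooled contrast nets the gain against the loss.

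The pooled rate is the only between-arm sodium estimate in the plan. A risk ratio near 1 could mean no effect on sodium or a shift with offsetting tails. A ratio below 1 could accompany more hypernatraemia. At stake is how metabolic tolerance is reported, not the efficacy result.

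**Working it through.** **Figures from the SAP.** Section 2.3 gives 35% v 50%, two-sided 5% error, 80% power and 170 per arm; section 2.2 gives 1:1 allocation. Check of the 170: n = [1.96·√(2×0.425×0.575) + 0.8416·√(0.35×0.65 + 0.50×0.50)]² / 0.15² = (1.370 + 0.582)² / 0.0225 ≈ 169.3, so 170. It is used here only as the number per arm. The SAP states no expected rate of low, high or pooled dysnatraemia.

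**The structure.** Let L and H be the proportions below 135 and above 155, with 0 for control and 1 for milrinone. Ignoring the few patients with both, the pooled risk ratio is

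RR = (L1 + H1)/(L0 + H0) = w·(L1/L0) + (1 − w)·(H1/H0), where w = L0/(L0 + H0).

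It is an average of the two component risk ratios, weighted by their control rates. If one is below 1 and the other above 1, the pooled value lies between them, and which side of 1 it falls on depends on w.

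**Assumed model (not from the SAP).** Each patient's lowest and highest sodium are normal with common SD s and correlation 0.5; treatment adds d to both.
- L = Φ((135 − mean lowest − d)/s)
- H = 1 − Φ((155 − mean highest − d)/s)
- Pooled = L + H − both, with the overlap from the bivariate normal

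**Main example:** means 138 and 146, SD 6, d = +3.
- Control: L = Φ(−0.5) = 0.3085; H = 1 − Φ(1.5) = 0.0668; both = 0.0032; pooled = 0.3721.
- Shifted: L = Φ(−1) = 0.1587; H = 1 − Φ(1) = 0.1587; both = 0.0038; pooled = 0.3136.
- Risk ratios: low 0.51, high 2.4, pooled 0.84.

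Unadjusted intervals at 170 per arm, with SE(log RR) = √[(1−p1)/(170·p1) + (1−p0)/(170·p0)]:
- High: SE = √(0.0312 + 0.0822) = 0.337, so RR 2.4 (1.2 to 4.6).
- Pooled: SE = √(0.0129 + 0.0099) = 0.151, so RR 0.84 (0.63 to 1.13).

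**Range over other assumptions:**

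| Mean lowest/highest, SD | Shift | <135 | >155 | Pooled | Pooled RR |
|---|---|---|---|---|---|
| 138/146, 6 | +3 | 31% → 16% | 7% → 16% | 37% → 31% | 0.84 |
| 139/147, 5 | +2 | 21.2% → 11.5% | 5.5% → 11.5% | 26.6% → 22.9% | 0.86 |
| 139/147, 5 | +4 | 21.2% → 5.5% | 5.5% → 21.2% | 26.6% → 26.6% | 1.00 |
| 138/146, 6 | −3 | 31% → 50% | 7% → 2% | 37% → 52% | 1.40 |
| 137/143, 5 | −3 | 34.5% → 57.9% | 0.8% → 0.1% | 35.3% → 58.1% | 1.65 |
| 142/150, 5 | +4 | 8.1% → 1.4% | 15.9% → 42.1% | 23.8% → 43.4% | 1.82 |

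In the first three rows the pooled ratio is at or below 1 while the rate above 155 at least doubles. In the last three it moves with the component that worsens. In the fifth row almost nothing is lost: 1.65 pooled against 57.9/34.5 = 1.68 for the low rate alone.

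**The case against.** The SAP is consistent with itself. It defines intolerance as leaving a sodium range in either direction and analyses exactly that. If the pooled rate falls, fewer patients left the range, which is the correct sign for the quantity defined. This stands: the point is an incomplete summary, not a contradiction.

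Direction is also partly covered by the daily minimum and maximum plots. The SAP does not say what they show. If they show means, an SD of 6 with 170 per arm gives a half-width of 1.96 × 6/√170 ≈ 0.9 mmol/L, so a 3 mmol/L shift would be visible. This largely stands. What the plots lack is a between-arm estimate of patients beyond each limit. Adverse-event data cannot be relied on to supply it, since section 5.4 leaves the recording of abnormal laboratory results to the investigator's view of relevance.

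The calculations assume a uniform shift. A drug acting on one tail only would not be cancelled, and one that widened both tails would have its effects added together by pooling. The normal model is also crude: in the main example the difference between highest and lowest has mean 8 and SD 6, so Φ(−8/6) ≈ 9% of simulated patients have a maximum below their minimum. The figures illustrate and do not predict.

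A reader might infer three stronger things that the document does not support:
- That pooling will hide harm or reverse its sign. This depends on baseline rates and on the size and direction of the shift, none of which the SAP gives.
- That the cut-offs are lopsided, so that low sodium must dominate. They lie 5 and 15 mmol/L from 140 but 10 and 10 from 145, and the SAP states neither a centre nor a sodium rate.
- That the trial loses power for a sodium test. Section 3.1 provides no p-value for a tertiary outcome.

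**Conclusion.** The point holds in a limited form. One pooled rate is the only between-arm sodium estimate, and under a one-way shift it understates the change to some degree. How much depends on distributions that have to be assumed: across the settings examined, the pooled risk ratio ran from 0.84, with hypernatraemia more than doubled, to 1.82, with the rise plainly visible. Cancellation or a favourable-looking ratio is therefore possible, not established.

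This is a minor matter for a tertiary safety outcome. It affects how tolerance is described and leaves the primary conclusion untouched. No view is taken on whether 135 and 155 mmol/L are the right limits.

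**What to change.** In sections 5.1.3 g) and 5.2.3 and in Table 1, keep the pooled rate if wanted and add two outcomes over the same treatment window: the proportion of patients with natraemia below 135 mmol/L and the proportion with natraemia above 155 mmol/L. Give each its own risk ratio and 95% confidence interval, with the cut-offs unchanged.

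The cost is a few words and two table rows. Daily minimum and maximum natraemia are already planned outputs, so no new data are needed. The downside is two more estimates, the rarer with a wide interval (1.2 to 4.6 in the main example); with very few events the adjusted model may not be estimable, and counts per arm should then be shown. Section 2.4 places publication of the SAP before database lock, so the addition should be made before lock; after unblinding it would be post hoc.

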5.2 Analysis Methods

Unless otherwise specified, all analyses will be completed on the intention to treat population.

 CHU ANGERS <small>CENTRE HOSPITALIER UNIVERSITAIRE</small>	 Statistical analysis plan	N° EudraCT 2019-002145-37 CT Number : 2024-515994-83-00 SAP V1.0 Date : 15/01/2026
---	--	---

The characteristics at inclusion and the measures of patient assessments for each treatment arm will be described using percentages or means, standard deviations, medians and interquartile ranges, and compared using Khi-square tests or Student t tests for respectively categorical and continuous data. A summary of the proposed analyses is presented in Table 1.

5.2.1 Primary Outcome:

Primary analysis:

The main statistical analysis will be performed on the intention to treat population using a binomial logistic regression model including as covariates the treatment arm and the different stratification factors for randomization (the center, the initial WFNS score dichotomized as <3 vs ≥ 3 and the patient's consciousness at inclusion).

Secondary analysis:

As a secondary analysis, we will report absolute risk reduction using a proportional odds approach, using the Brant-Wald test at the alpha level of 5%, which may be more sensitive for detecting a shift over the entire spectrum of outcome (mRS 7-point ordinal scale).

Sensitivity analysis:

An other model will be proposed based on the ITT population, including in addition to the covariates already considered the level of consciousness and the delay before performing angiography (within 12 hours or not), and the interactions between these two covariates and the treatment arm, to assess a possible variation in the treatment effect according to the status on these two covariates

These two models will be performed on the per-protocol population as an evaluation of the robustness of their results. In any cases, the primary analysis results will be authoritative.

5.2.2 Secondary Outcomes:

- The analysis of the mRS, the extended GOS and the EQ-5D score at 3 and 6 months will be performed considering (ordinal) proportional odds models, based on the same set of covariates.
- The ICU mortality and 6 months mortality will be analyzed using Cox models based on the same set of covariates. The validation of these models will be evaluated by analyzing Schoenfeld residuals.

 CHU ANGERS <small>CENTRE HOSPITALIER UNIVERSITAIRE</small>	 Statistical analysis plan	N° EudraCT 2019-002145-37 CT Number : 2024-515994-83-00 SAP V1.0 Date : 15/01/2026
---	--	---

5.2.3 *Tertiary outcomes*

- The analysis of angiographic successes at day 7 and 14 will be performed considering (ordinal) proportional odds models, based on the same set of covariates
- The proportion of therapeutic arteriography between each group and the median number of arteriography will be compared.
- The analysis of hospital length of stay will be carried out by using linear regression models based on the same set of covariates.
- Patients outcomes and treatment tolerance will be analyzed using logistic models for dichotomous data (transfer to a convalescent center, patients living at home at 3 and 6 months, need to initiate or to increase the catecholamine doses by 50%, occurrence of dysnatremia), or linear regression models for continuous data (DAAH90, daily dose of catecholamines, average daily urine output).

5.2.4 *Pre-planned sub-group analysis*

We plan exploratory subgroup analyses for the primary outcome (as described above) in the following sub-groups:

- Sex: female sex versus male sex. We hypothesize no treatment effect difference between male and female sex.
- Initial WFNS score <3 vs ≥ 3 . We hypothesize that the treatment effect is more important in the less severe patients (WFNS <3).
- Consciousness level at inclusion: conscious vs unconscious. We hypothesize that the treatment effect is more important in the less severe patients (conscious patients).

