2.3 Sample Size

We estimated that the rate of favorable neurological outcomes (defined as a mRS ≤ 2) at 3 months in patients with vasospasm following acute aSAH without milrinone infusion is approximately 35%. (This percentage was estimated based on the analysis of data extracted from the ATLANREA database, including 436 patients in 3 years, ClinicalTrials.gov - identifiant : NCT02714387) The proportion of favorable outcomes reported in case series of patients with vasospasm treated with milrinone is between 50 and 60%. For our sample size calculation, we thus hypothesized a percentage of favorable outcomes at 3 months of 35 and 50% respectively in the control and milrinone group. Considering a two sided test and a type I and type II error rates of 5 and 20%, the sample size required is 340 (170 patients in each group). Considering a 5% proportion of withdrawals, we planned to include 360 patients, and increased this number to 370 to compensate for patients included but not randomized because of early withdrawal.

 CHU ANGERS <small>CENTRE HOSPITALIER UNIVERSITAIRE</small>	 Statistical analysis plan	N° Eudract 2019-002145-37 CT Number : 2024-515994-83-00 SAP V1.0 Date : 15/01/2026
---	--	---

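### Age is collected at baseline but enters no outcome model, so the primary test forgoes a small, assumption-dependent amount of power; the planned analysis itself is valid

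*SAP*

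**What the plan says.** SAP 5.2.1 fits the primary endpoint (mRS ≤2 at 3 months) by logistic regression "including as covariates the treatment arm and the different stratification factors for randomization". Those factors are centre, initial WFNS in two classes (<3 vs ≥3) and consciousness at inclusion. They match the minimisation factors in 2.2. Sections 5.2.2 and 5.2.3 carry the set over to the secondary models and most tertiary ones, and the adjustment column of Table 1 repeats it.

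Section 4.3 shows what else is available: "Baseline characteristics of randomized patients include age; sex, comorbidities, usual medication", and, later in the same list, the initial WFNS score and Fisher class.

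The sensitivity model in 5.2.1 is described as "including in addition to the covariates already considered the level of consciousness", plus the delay before angiography and the interaction of each with treatment. Consciousness is already in the primary model. Neither age nor the ungrouped WFNS grade is added there. Sex appears only as a subgroup (5.2.4). Change from baseline is used for EQ-5D (5.1.2), which does not bring in age.

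**The concern.** Adjusting a binary-outcome model for a prognostic baseline covariate usually raises the power of the treatment test, whether or not the arms are balanced on it. Age is a natural candidate for functional recovery after haemorrhage, it is already in the database, and it is not a minimisation factor. The SAP is silent on it. Because the sample size gives 80% power with little to spare, a free gain is worth considering.

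There is also a practical point. Section 5.2 plans significance tests of baseline characteristics between arms but does not say what follows if they differ. If age happened to differ, any age-adjusted result would be post hoc and open to challenge. Naming age now avoids that argument.

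**Working it through.** **1. Reproduce the plan's figure.** Section 2.3 assumes "a percentage of favorable outcomes at 3 months of 35 and 50% respectively in the control and milrinone group", two-sided 5% and 80% power. With the pooled-variance formula and no continuity correction:

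n per arm = [1.960·√(2·0.425·0.575) + 0.842·√(0.35·0.65 + 0.50·0.50)]² / 0.15² = (1.370 + 0.582)² / 0.0225 = 169.3, so 170.

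This matches: "the sample size required is 340 (170 patients in each group". Power at 170 per arm is 80.2%. Allowing for 5% loss, 340/0.95 = 358, against 360 planned. The calculation uses no covariates, so the covariate set does not affect it.

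**2. Inputs for the comparison.** The 35% and 50% marginal rates and N = 340 are from the SAP. The rest are assumptions, because the SAP gives none:
- WFNS grades 1 to 5 in 30/20/10/18/22% of patients.
- Unconscious in 15/25/45/70/85% of those grades, lowering the log-odds of good outcome by 0.5.
- Age effect (log-odds per SD): 0.2 weak, 0.5 moderate, 0.8 strong. These are odds ratios of 0.82, 0.61 and 0.45 per SD.
- WFNS effect (log-odds per grade): 0.2, 0.35 and 0.5 respectively.
- Centre not modelled.

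**3. Method.** Logistic models were fitted to one very large simulated data set and scaled to N = 340. Power = Φ(λ − 1.96), where λ = log-odds ratio / SE. Effective-sample ratio = (λ_new/λ_SAP)².

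| Prognosis | Power, SAP set | + age | Effective N from age | + age and five-level WFNS |
|---|---|---|---|---|
| Weak | 81.0% | 81.2% | +0.6% (2 patients) | 81.4% |
| Moderate | 82.3% | 83.9% | +4.3% (15) | 84.2% |
| Strong | 83.7% | 87.1% | +10.4% (35) | 87.7% |

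Patient numbers are 340 × 0.006, 0.043 and 0.104.

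**4. What five-level WFNS adds beyond age.** The table shows 0.2, 0.3 and 0.6 points before any small-sample cost of three extra parameters. In 1,500 simulated trials of 340 patients per scenario, where that cost is paid, power went from 82.6 to 82.3%, 84.2 to 83.9% and 89.1 to 89.3%, which is indistinguishable from no change.

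**5. Where the gain shows.** In the moderate case the SE of the conditional log-odds ratio rises from 0.234 to 0.240 when age is added. From λ = 1.96 + Φ⁻¹(power), λ is 2.887 and then 2.950, so the log-odds ratio moves from 2.887 × 0.234 = 0.676 to 2.950 × 0.240 = 0.708. The estimate grows faster than its SE: (2.950/2.887)² = 1.044, agreeing with +4.3% up to rounding. On the marginal scale, the variance of the standardised risk difference fell by 0.9%, 5.7% and 12.5% across the three scenarios (variance ratios 0.991, 0.943 and 0.875).

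**6. A second set of assumptions.** 8,000 trials per scenario, 342 analysed (360 × 0.95), age odds ratios 0.75/0.65/0.55 per decade with an assumed SD of 12.5 years. Adding age moved power from 84.5 to 85.7%, 85.2 to 86.8% and 85.5 to 88.7%, gains of 1.2, 1.6 and 3.2 points. By [(1.96 + z_new)/(1.96 + z_SAP)]² − 1, these are 3.5%, 4.8% and 10.4% more patients. Five-level WFNS on top of age added 0.2 points each time. Type I error was 4.7% for the SAP set and 5.2% for the model with age and five-level WFNS. With a Monte Carlo SE of √(0.05·0.95/8000) = 0.24 points, both are compatible with 5%.

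**The case against.** The strongest reply is that nothing here is an error. Adjusting for every minimisation factor is sound practice, type I error is held, and under the assumptions above the planned model already exceeds 80% power. That stands: this is a missed opportunity.

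It is also fair that the size rests on assumed prognostic strengths, and that under weak prognosis the gain is about two patients' worth. The difference in simulated type I error, if it were real, would account for about one power point near 85% power. It is within simulation error, but the smaller gains should not be read to the decimal.

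Four stronger readings are tempting, and the documents do not support them:
- *The trial is underpowered or its sample size wrong.* The 340 reproduces without covariates.
- *The plan's intervals are needlessly wide throughout.* For the conditional odds and hazard ratios from the logistic, proportional odds and Cox models, adjustment need not shrink the SE, and in step 5 it rises. Table 1's mean differences for GOSE and EQ-5D are a different case, but no secondary outcome was calculated.
- *A chance age imbalance biases the result.* Chance imbalance is already allowed for in the standard error, and simulated type I error shows no inflation.
- *Cutting WFNS in two discards important information.* WFNS is coarsened, not absent, and the finer grades add next to nothing once age is in.

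Replacing the sensitivity model because it repeats consciousness would also be a mistake. Its purpose is to examine treatment interactions, and those should stay. Finally, the protocol is not at hand and may also fix the primary model, in which case the texts would need aligning.

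**Conclusion.** The point holds as a worthwhile, inexpensive improvement. Age is in the baseline data and in no outcome model. Adding it would gain about 0 to 3 power points for the primary test, or roughly 1 to 10% more effective patients. The range depends on assumed strengths for age, WFNS and consciousness and on an assumed WFNS distribution, with centre left out. If age is only weakly prognostic, the gain is negligible.

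The covariate list is certain from the text; the size of the loss is not. The benefit is argued for the functional and mortality outcomes and was computed only for the primary one.

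**What to change.** Before database lock and unblinding (2.4 places publication of the SAP before lock):

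1. In 5.2.1 and the primary row of Table 1, set the covariates to treatment, centre, WFNS class (<3 vs ≥3), consciousness and age as a continuous variable. Five-level WFNS is optional.
2. Use the same set for the mRS, GOSE, EQ-5D and mortality models. The tolerance endpoints need not change.
3. Fit the primary model as logistic regression, as 5.2.1 already says, and obtain the risk ratio or risk difference by standardisation. Table 1 names a log-binomial model, which may not converge with a continuous covariate.
4. Report the three-factor model as an added sensitivity analysis, and keep the existing interaction model with consciousness and angiography delay.

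Cost: revised wording, one degree of freedom, and a conditional odds ratio of slightly different size from the three-factor one. No new data are needed.
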